#### Statistical power calculation

- *A previously published sample size calculation based on a Phase I study suggests that a trial of 80 participants (40 in each arm) would have 80% power with  $p < 0.05$  to detect a reduction in autoimmune adverse events from 40% down to 10%.*
- *Primary analysis will be based on observed data only but a sensitivity analysis where missing data is imputed using maximum likelihood imputation methods will be undertaken.*
- *All statistical analyses will be conducted by our in-house statisticians, [name] and A/[name].*

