## 1. Background

Multiple sclerosis (MS) is the commonest cause of neurological disability in young adults, and particularly affects women. Left untreated, MS causes marked difficulty walking or inability to walk in more than half after 20-30 years. This dire prognosis has been radically altered by the advent of a variety of effective therapies, including three highly effective infusion therapies.

Alemtuzumab is a highly effective therapy for the treatment of MS. In pivotal phase III clinical trials (CARE-MS I and II) alemtuzumab reduced the risk of relapse by 51-55% (Class I evidence) and sustained disability by 30-42% (Class I evidence) when compared against a proven, active-comparator, therapy in the form of interferon beta 1a. This novel therapy is administered as two courses, the first over 5 days and the second course over 3 days, 12 months later. In the majority (53%) of people with MS (pwMS) treated with alemtuzumab no further therapy was required over 8 years of follow up. The annual cost of alemtuzumab is similar to other highly effective therapies for MS (around \$30,000 per year). Because only two years of therapy is required in most pwMS and rarely are more than three courses given, the recurring costs of this therapy are considerably less than other similarly efficacious therapies (natalizumab and ocrelizumab) which have to be administered on a recurring basis seemingly indefinitely. However, the use of alemtuzumab as a therapy in pwMS has been relatively limited and this is in large part because of a significant risk of autoimmune adverse events. Autoimmune thyroid disease occurs in approximately one-third of patients and idiopathic thrombocytopenia (2%) and anti-GBM renal disease (0.5%) are seen less commonly, together with a variety of other occasional autoimmune diseases that have been described. It has been noted that this phenomenon is specifically seen in MS and does not occur as frequently in other indications for this therapy.

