## 3. Methods

### a. Methodological Approach

- *This will be a 3-year, multi-centre, double-blinded, randomised (2:1), placebo-controlled trial of rituximab versus placebo in pwMS being treated with alemtuzumab.*
- *Participants will be recruited from one of six hospitals across Queensland, Gold Coast University Hospital, Royal Brisbane and Women's Hospital, Mater Hospital Brisbane, Princess Alexandra Hospital, Sunshine Coast University Hospital and Townsville Hospital and Health Service.*
- *The study would aim to recruit patients over 24 months and follow individual participants for a minimum of 2 years.*

---

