## c. Study Population

- *The study will aim to recruit 80 pwMS who are due to commence treatment with alemtuzumab.*
- *Inclusion criteria*
  - *Aged 18 – 55 years (inclusive)*
  - *Diagnosed with relapsing remitting MS (RRMS) by a neurologist*
  - *Diagnosis of MS meeting 2017 McDonald criteria*
  - *Diagnosed with MS within the previous 10 years*
  - *Expanded disability status scale (EDSS) score < 5.0*
  - *English speaking or non-English speaking who can ensure external interpreter assistance (e.g. relative or friend) to attend all visits for the duration of the clinical trial.*
  - *Available to attend clinic visits*
  - *Willing to sign up for and comply with Bloodwatch monitoring program*
  - *Fully vaccinated against COVID-19 (2 standard doses plus booster)*
- *Exclusion criteria*
  - *Known or suspected prior autoimmune disease (other than MS)*
  - *Any other serious co-morbidity that in the view of the investigator would preclude participation in the study*
  - *Pregnant (if female)*
  - *Currently lactating (if female)*

- 
- Unwilling or unable to use appropriate contraception for the treatment phase of the study (2 years) – male or female
  - Recent or current history of major depression, bipolar disorder, psychosis or suicidality
  - Currently or recently taking any illicit substances (including any cannabis product)
  - Allergy to valaciclovir
  - Allergy to Bactrim, Trimethoprim or Sulphur based antibiotics

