#### **d. Recruitment/ Selection**

- *Potential participants will be recruited through the MS or CNS inflammatory disease clinics of the six participating hospitals with a cap of 20 participants at any single centre. Participants will not be financially compensated for their involvement in this trial but will be reimbursed for any reasonable costs of participation (e.g. parking costs).*
- *Participants will be recruited by neurologists at each site, who having identified a patient who is about to commence treatment with alemtuzumab, will invite the pwMS to participate in the trial. Potential participants will be provided with an introduction and overview of the study by their treating neurologist. Those who are interested in participating will be provided with the Patient Information and Consent Form (PICF) to take away and read and a further visit with one of the study investigators will be arranged at a later date.*
- *Participants will be enrolled in the study at the baseline/screening visit provided they:*
  - 1. *Have given written informed consent*
  - 2. *Meet all the inclusion criteria*
  - 3. *Meet none of the exclusion criteria*
- *Randomisation: Participants will be randomised at enrolment to treatment with rituximab or placebo at a 2:1 ratio. Randomisation will be performed using the randomisation module of the REDCap database based on a random number sequence produced in Excel®, Microsoft (Seattle, CA, USA) stratified by site, sex and age. This randomization sheet will be generated by Assoc/[name]. There will a cap of 20 participants for any single site.*
- *Blinding and allocation concealment: This will be a double-blinded study with both patient and treating physician blinded as to whether the participant is receiving active treatment or placebo. At the screening visit, participants will be assigned a unique participant Screening Number. At the baseline/enrolment visit, after eligibility is confirmed and the full consent form has been signed, a Participant Identification Number (PIDN) will be assigned. PIDNs will be randomly assigned to intervention or placebo groups according to the randomisation code provided by the randomisation sheet. Randomisation*

---

codes will only be visible through REDCap to site pharmacists who will make up the active treatment and placebo. Both rituximab and 0.9% sodium chloride (placebo) are colourless fluids, so will be indistinguishable to treating physician, participants and other staff.

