## **f. Risk Mitigation Procedures**

- *Treatment with alemtuzumab is associated with a risk (6-8%) of reactivation of HSV2 infection during the first month and a much lower level risk of listeria meningitis over the same time period. As is our usual practice all participants will receive valaciclovir 500 mg once daily for 30 days and Bactrim DS 960mg three times per week for 4 weeks commencing on the first day of therapy.*
- *In view of the potential additive risk of rituximab and alemtuzumab causing an increased risk of infection all participants will be advised to report any symptoms of fever, headache, neck stiffness, photophobia, shortness of breath, cough, abdominal pain or skin lesions to site investigators immediately.*
- *In view of the known risk of autoimmune adverse events with alemtuzumab (e.g. 30% risk of autoimmune thyroid disease) all participants will be monitored with monthly blood and urine tests through the Bloodwatch program. This is PBS mandated online monitoring program for all pwMS undergoing therapy with alemtuzumab which is sponsored by the manufacturer. This is standard of care for this therapy and includes monthly urine tests for red cells and protein, monthly blood tests for full blood count, urea and electrolytes and 3-monthly blood tests for TSH levels.*
- *Regular lymphocyte subset counts will be monitored and rituximab administration will be delayed if B-cell counts do not exceed 30% of pre-treatment levels.*

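### The power statement describes 40 participants per arm, but the trial randomises 2:1 (about 53 and 27) with a Cox primary analysis, so no power is given for the actual design

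*Protocol*

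**What the plan says.** The Protocol's Study Population section sets the size: "The study will aim to recruit 80 pwMS who are due to commence treatment with alemtuzumab". The allocation is given in Methodological Approach, which describes a "double-blinded, randomised (2:1), placebo-controlled trial of rituximab versus placebo", and in Recruitment/Selection: "Participants will be randomised at enrolment to treatment with rituximab or placebo at a 2:1 ratio". The legend of Figure 1 repeats the 2:1 ratio.

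The Statistical power calculation paragraph relies on a published calculation from a Phase I study, under which "a trial of 80 participants (40 in each arm) would have 80% power" at p < 0.05 for a fall from 40% to 10%. It does not adapt that calculation to this trial.

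Data Analysis and Statistical Considerations makes the primary analysis a Cox model for onset of an autoimmune adverse event, because follow-up will differ between participants.

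On background risk, section 1 gives about one-third for thyroid disease, 2% for thrombocytopenia and 0.5% for anti-GBM disease, and mentions other occasional autoimmune diseases without a rate. Risk Mitigation Procedures cites a "30% risk of autoimmune thyroid disease". The primary outcome counts all of these, including any other autoimmune disease.

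**The concern.** Eighty participants cannot be both 40 per arm and 2:1. The placebo arm, which is expected to supply most of the events, will have about 27 people, a third fewer than the power paragraph says. The paragraph also describes a comparison of two proportions, whereas the primary test is time-to-event. An ethics committee or a later reader is thus given an arm size that will not exist and a power figure for another design.

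The 40% placebo rate matters as well. It is higher than the sum of the rates the protocol quantifies, and the paragraph does not explain the gap. If the true rate is lower, a non-significant result could be read as coming from an adequately powered trial when it did not.

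**Working it through.** **Inputs.** N = 80, 2:1 allocation, 40% against 10%, p < 0.05 and 80% power, all from the protocol. The power paragraph does not say one- or two-sided; two-sided is assumed.

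**1. Reproduce the stated figure (1:1).**
n per arm = [1.960·√(2·p̄·(1−p̄)) + 0.842·√(p₁(1−p₁) + p₂(1−p₂))]² / (p₁−p₂)², with p̄ = 0.25.
= [1.960·√0.375 + 0.842·√0.33]² / 0.09 = (1.200 + 0.483)² / 0.09 ≈ 31.5, so 32 per arm.
With the continuity correction, n′ = (n/4)·[1 + √(1 + 4/(n·0.3))]² = (31.5/4)·(2.193)² ≈ 37.9, so 38 per arm. Fisher's exact test needs 36. The published 40 per arm is therefore reproduced, slightly on the safe side.

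**2. Actual arm sizes and events.** 80 × 2/3 ≈ 53 and 80 × 1/3 ≈ 27. Expected events: 27 × 0.40 + 53 × 0.10 ≈ 16, against 40 × 0.40 + 40 × 0.10 = 20 at 1:1.

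**3. Power at 40% against 10%, two-sided 5%.** The Pearson, Fisher and Yates rows are exact enumerations. The log-rank row is simulated with exponential event times and common follow-up.

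| Test | 40:40 | 53:27 |
|---|---|---|
| Pearson | 90% | 88% |
| Fisher | 85% | 85% |
| Yates | 84% | 81% |
| Log-rank, simulated | 90% | 89% |
| Schoenfeld formula | 94% | 85% |

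The continuity-corrected normal formula, a rougher version of the Yates row, gives 79.9% at 53:27, which is 80% to the nearest point.

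The Schoenfeld row uses HR = ln(0.9)/ln(0.6) = 0.206 and power = Φ(|ln HR|·√(D·π(1−π)) − 1.960). At 2:1: Φ(1.579·√(16 × 2/9) − 1.960) = Φ(1.017) = 84.5%. At 1:1: Φ(1.579·√(20 × 1/4) − 1.960) = Φ(1.570) = 94.2%. Simulation does not confirm this drop of about 10 points; the simulated loss is about 1 point. The approximation is poor for so strong an effect with few events and unequal arms.

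**4. Sensitivity to the placebo rate (53:27, simulated log-rank).** The sum of the quantified rates is about 33% + 2% + 0.5% = 35.5% if no one has two of the diseases.

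| Placebo rate | Rituximab held at 10% | 75% relative reduction kept |
|---|---|---|
| 35.5% | about 79% | about 83% |
| 33.3% | about 73% | about 80% |
| 30% | about 63% | about 75% |

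At 1:1 with rituximab held at 10%, the corresponding figures are about 81%, 74% and 63%. The lower placebo rate causes the fall, and the allocation adds about a point at most.

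**The case against.** The strongest reply is that the error has little consequence. At the protocol's own 40% against 10%, the stated 80% holds under 2:1, and Fisher's test gives the same power for both allocations. That stands.

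A reader might infer that 2:1 allocation is what takes the trial below 80% power. The documents do not support this. Only the Schoenfeld formula shows a large allocation loss, and simulation of the test that matches the planned analysis does not.

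A reader might also infer that the protocol's own background figures show the trial to be underpowered. This goes too far as well. The 30% and one-third figures cover thyroid disease only, while the endpoint is any autoimmune disease, so they are lower bounds for the placebo rate. Even 35.5% leaves out the diseases without a rate. At 35.5% to 36% the shortfall is marginal (simulated log-rank about 79% to 81%), and it disappears if the 75% relative reduction is kept. The 40% comes from a cited source that is not at hand, so it is unexplained here rather than contradicted.

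A dropout allowance may be set out in a statistical analysis plan and is not counted against the protocol. What the objection leaves untouched is that 40 per arm is false for this trial and is the only support given for its size.

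**Conclusion.** The point holds as an internal contradiction: the power paragraph describes a 1:1 comparison of proportions, while the trial is 2:1 with a Cox analysis. The placebo arm will be about 27, not 40, and expected events about 16, not 20.

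The contradiction does not overturn the 80% claim at the stated assumptions, where power at 53:27 is about 81% to 89% by test. The remaining weakness is dependence on a 40% placebo rate that the protocol does not reconcile with its own figures. How much power is lost below 40% depends on whether rituximab is held at 10% or the relative reduction is held at 75%. These results assume a two-sided 5% test, exponential event times, common follow-up and no losses.

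**What to change.** In the Statistical power calculation paragraph:

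- Delete the 40-per-arm wording and restate the calculation for 80 participants randomised 2:1 (53:27), with a two-sided 5% log-rank or Cox test and event proportions tied to a stated follow-up time. Under the simulation assumptions above, this gives about 16 events and about 89% power at 40% against 10%.
- Justify the 40% placebo rate against the rates in Background and Risk Mitigation Procedures, saying what the other autoimmune diseases are assumed to add.
- Add sensitivity figures for placebo rates of 35.5%, 33.3% and 30%, from simulated log-rank rather than the Schoenfeld formula, and state which effect is held fixed: about 79%, 73% and 63% with rituximab at 10%, or about 83%, 80% and 75% with the 75% relative reduction.

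The cost is wording only, with no extra participants. The downside for the sponsor is a visibly lower power at placebo rates below 40%.

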#### 4. Translation to Changes in Clinical Practice

- *A successful outcome to this clinical trial would pave the way to more widespread use of alemtuzumab for the treatment of multiple sclerosis. If a significant reduction in the frequency of autoimmune adverse events is seen with the co-administration of rituximab with alemtuzumab this would remove the one major barrier to the use of this highly effective therapy. Such an outcome would remove or significantly reduce the morbidity and risk of serious adverse outcomes associated with autoimmune adverse events. It might even lead to the removal of or a less onerous form of ongoing monitoring for autoimmune adverse events after alemtuzumab administration. More widespread use of alemtuzumab would have considerable benefits to pwMS and healthcare providers. Treatment with alemtuzumab involves two brief courses of treatment 12 months apart and then for many nothing ever again. This compares favourably with all other approved forms of therapy for MS*

which are essentially indefinite or at least until a significantly advanced age is reached (e.g. age 65 years). This means that issues of medication compliance, venous access, treatment fatigue and the time and resource commitments are all reduced. It also means that pwMS can get on with the rest of their life, have a family and not have to worry about ongoing treatment. For health services the overall costs of alemtuzumab are considerably less. The lifetime costs of treatment with the currently approved therapies for MS are compared in Table 4, assuming a mean age of onset of 32 years for relapse-remitting MS and treatment to age 65 years.

**Table 4. Comparison of Projected MS treatment costs (data from PBS, Australia)**

Treatment	Annual cost	Years of therapy	Total cost
Alemtuzumab	\$54,121.50/\$32,472.90	2	\$86,594.40
Ocrelizumab	\$35,161.48	33	\$1,160,328.84
Natalizumab	\$16,088.16	33	\$530,9009.28
Fingolimod	\$26,633.40	33	\$878,902.20
Siponimod	\$26,633.40	23	\$612,568.20
Cladribine*	\$27,153.60	2 (+?)	\$54,307.20
Dimethyl fumarate	\$15,500.88	33	\$511,529.04
Beta-interferon	\$12,018.36	33	\$396,605.88
Copaxone	\$10,739.76	33	\$354,412.08

\* = based on 70 kg person

- This would make alemtuzumab arguably the most effective therapy for MS and the cheapest. Only cladribine is cheaper for the first two years of therapy, but further relapses and additional treatment is required over a 3-year time frame in 60% of patients. Additional treatment with alemtuzumab is required in 30-40% of cases but this treatment is provided for free by the manufacturer in Australia. When compared to all other treatments for MS, across the 25,000 pwMS in Australia this would amount to a cost saving of between \$133 and \$536 million annually, assuming that 2/3 of pwMS are on treatment.
- The outcomes from this research will be disseminated in the following ways:
- It is anticipated that the results of this clinical trial will be published in a leading neurology or general medical journal.

- *CIA is the leading author of the Australian and New Zealand treatment guidelines for MS which are periodically updated. The outcomes of this study will be incorporated into those guidelines.*
- *This trial will be registered with the Australia and New Zealand Clinical Trials Registry and as a Clinical Trial Notification with the Therapeutics Goods Administration.*
- *Findings from this study will likely be presented at local (ANZAN) and International (AAN and ECTRIMS) scientific meetings.*
- *Outcomes from this trial will be presented in lay form through the Griffith University Facebook page.*

## 5. Timeline

- *It is proposed that this clinical trial will be conducted over a 5-year time span. All necessary regulatory approvals, HREC approval and funding will be sought in 2021, with a proposed start date for the trial in January 2022. Recruitment of participants will span the first 2 years and follow will continue for a minimum of 2 years and 6 months (maximum of 4 years and 6 months). The analysis will be undertaken in the final 5 months. Please see Gant chart of proposed timeline in Table 5.*

**Table 5. Gant chart of proposed timeline.**

Year	2021	2022	2023	2024	2025	2026
HREC App	■					
Funding App	■					
CTN App	■					
Site initiation		■				
Recruitment		■	■			
Enrolment		■				
Trial		■	■	■	■	■
Analysis						■

## 6. Funding and Resources

- *Funding for this project is to be sought in 3 ways:*
- *An application for NMHRC MRFF grant funding to cover the entire project.*
- *Applications to MSRA for both a project grant and a PhD fellowship to fund at least part of the project.*
- *Applications to local funding bodies (e.g. Gold Coast Foundation).*
- *Possible combinations of the above and local hospital funding applications.*
- *Several funding envelopes are to be considered but a minimum of \$102,114.16 would be required to enroll 20 participants.*

---

